4.2.2.1 Objective Response Rate

Objective Response Rate (ORR) is defined as the number of treated subjects who achieve a best response of complete response (CR) or partial response (PR) based on investigator assessments (using RECIST v1.1 criteria) divided by the number of all treated subjects. Best Overall Response (BOR) is defined as the best response, as determined by the investigator, recorded between the date of first treatment and the date of objectively documented progression per RECIST v1.1 criteria or the date of subsequent therapy, whichever occurs first. For subjects without documented

progression or subsequent therapy, all available response designations will contribute to the BOR determination. Confirmation of response is required at least 4 weeks after the initial response.

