4.2.2.2 Duration of Response

Duration of Response (DOR) is defined as the time between the date of first documented response (CR or PR) to the date of the first documented tumor progression as determined by the investigator (per RECIST v1.1 criteria), or death due to any cause, whichever occurs first. Subjects who start subsequent therapy without a prior reported progression will be censored at the last evaluable tumor assessments prior to initiation of the subsequent anticancer therapy. Subjects who die without a reported prior progression will be considered to have progressed on the date of their death. Subjects who neither progress nor die, DOR will be censored on the date of their last evaluable tumor assessment. DOR will be evaluated for responders (confirmed CR or PR) only.

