4.2.3.2 Duration of Response

Duration of Response (DOR) is defined as the time between the date of first documented response (sCR, CR, VGPR or PR) to the date of the first documented tumor progression as determined by the investigator (per IMWG Response criteria), or death due to any cause, whichever occurs first. Subjects who start subsequent therapy without a prior reported progression will be censored at the last evaluable tumor assessments prior to initiation of the subsequent anticancer therapy. Subjects who die without a reported prior progression will be considered to have progressed on the date of their death. Subjects who neither progress nor die, DOR will be censored on the date of their last evaluable tumor assessment. DOR will be evaluated for responders (confirmed sCR, CR, VGPR or PR) only.

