8 CONVENTIONS

The following conventions may be used for imputing partial dates for analyses requiring dates:

- For missing and partial adverse event onset dates, imputation will be performed using the Adverse Event Domain Requirements Specification¹
- For missing and partial adverse event resolution dates, imputation will be performed as follows (these conventions may change):
 - If only the day of the month is missing, the last day of the month will be used to replace the missing day. If the imputed date is after the death date or the last known alive date, then the latest known alive date or death date is considered as the resolution date.
 - If the day and month are missing or a date is completely missing, it will be considered as missing.
- Missing and partial non-study medication domain dates will be imputed using the derivation algorithm described in 4.1.3 of BMS Non-Study Medication Domain Requirements Specification².
- For death dates, the following conventions will be used for imputing partial dates:
 - If only the day of the month is missing, the 1st of the month will be used to replace the missing day. The imputed date will be compared to the last known alive date and the maximum will be considered as the death date.
 - If the month or the year is missing, the death date will be imputed as the last known alive date.
 - If the date is completely missing but the reason for death is present, the death date will be imputed as the last known date alive.

- For date of progression after start of study therapy, the following conventions will be used for imputing partial dates:
 - If only the day of the month is missing, the 1st of the month will be used to replace the missing day. In case of the date of death is present and complete, the imputed progression date will be compared to the date of death. The minimum of the imputed progression date and date of death will be considered as the date of progression.
 - If the day and month are missing or a date is completely missing, it will be considered as missing.
- For date of progression to prior therapies, the following conventions will be used for imputing partial dates:
 - If only the day of the month is missing, the 1st of the month will be used to replace the missing day.
 - If the day and month are missing or a date is completely missing, it will be considered as missing.
- For other partial/missing dates, the following conventions were used:

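### The SAP's rule for a progression date with a missing day has no lower bound, so progression can be dated before a confirmatory or progression-free assessment in the same month

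*SAP*

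**What the plan says.** SAP Section 8 gives one rule for a progression date after the start of study therapy when the month is known: "If only the day of the month is missing, the 1st of the month will be used to replace the missing day". If a complete death date exists, the imputed date is compared with it: "The minimum of the imputed progression date and date of death will be considered as the date of progression". No other comparison is specified.

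The death-date rule in the same section also starts from the 1st of the month, but it is protected from below: "The imputed date will be compared to the last known alive date and the maximum will be considered as the death date". The rule for adverse event resolution dates imputes forward, to the last day of the month, and is protected from above by the death date or last known alive date.

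Two endpoints use the progression date. Duration of response (SAP Sections 4.2.2.2 and 4.2.3.2) runs from first documented response to first documented progression or death, for confirmed responders only. For solid tumors, best overall response (SAP Section 4.2.2.1) counts only assessments between first treatment and "the date of objectively documented progression per RECIST v1.1 criteria or the date of subsequent therapy, whichever occurs first". The corresponding myeloma section, 4.2.3.1, states no such window.

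**The concern.** A check on an imputed date should guard the side on which the imputation can err. Replacing a missing day by the 1st errs only backward, yet the progression rule guards only against a date that is too late. Nothing stops the imputed date from falling before an assessment, earlier in the true sequence but in the same month, at which the subject had not progressed.

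At stake is the row for one responder in the efficacy listing. Duration of response would be understated. For a RECIST responder, the confirmatory scan could fall outside the window for best overall response, so that the response looks unconfirmed. The error always runs toward a shorter or lost response, and the contradiction would have to be settled after the data are seen.

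**Working it through.** The plan states no figure on this point, so there is nothing to reproduce. The inputs are the Section 8 rule and the protocol's assessment schedules.

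**1. Size of the shift.** A true date on day D of a month moves back D − 1 days. Over a 365-day year the total shift is 7 × 465 + 4 × 435 + 378 = 5,373 days. The mean is 5,373/365 = 14.7 days and the maximum is 30.

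**2. The existing check.** If progression precedes or coincides with death, the 1st of the progression month cannot fall after death. The minimum is then always the 1st, and the comparison with death never changes anything.

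**3. When a collision occurs.** Let the previous assessment be g days before true progression on day D. The imputed date is strictly before that assessment when D ≥ g + 2, and on or before it when D ≥ g + 1. This counts every calendar date once as the true progression date:

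| Gap g (days) | Imputed date strictly before the assessment | Largest reversal |
|---|---|---|
| 14 | 185/365 = 50.7% | 16 days |
| 24 | 65/365 = 17.8% | 6 days |
| 28 | 18/365 = 4.9% | 2 days |
| 29 | 7/365 = 1.9% | 1 day |
| 30 or more | 0 | none |

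For g = 28 the strict cases are progression on a 30th (11 dates) or a 31st (7 dates). Adding the 29ths gives the on-or-before count. Over four years that is 45 + 44 + 28 = 117 of 1,461 dates, or 8.0%.

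**4. Cohort C2, on schedule.** Protocol Table 2-2 sets M-protein tests every 2 cycles of 14 days, so g = 28 (24 at the 12-day minimum dosing interval). Take a response on 5 April, confirmed on 3 May, with progression on 31 May. The imputed date is 1 May, before the confirmation. Listed duration is 26 days instead of 56. Corrected calcium, a progression criterion in Appendix 11, is collected every cycle (Protocol Section 9.1.2.1), so progression by calcium can follow confirmation after 14 days.

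**5. Solid tumors.** Scans are every 56 ± 7 days at first (Protocol Section 9.1.1.1), so consecutive scheduled scans are 42 to 70 days apart, beyond the 30-day maximum shift. On scheduled scans alone no collision is possible. SAP Section 4.2.2.1 requires confirmation at least 4 weeks after response, and Appendix 10 lets the next scheduled scan serve without requiring it. With confirmation at 28 days, the next scheduled scan follows nominally 56 − 28 = 28 days later and at the earliest 42 − 28 = 14. Take a response on 7 March, confirmed on 4 April, with progression on 25 April. The imputed date is 1 April, so the confirmatory scan falls after the window closes. Duration, if still listed, is 25 days instead of 49.

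**6. Can duration be negative?** In C2 on schedule, confirmation is at 28 days and M-protein progression no earlier than 56, or 42 by calcium. At the minimum dosing interval these become 24 days for confirmation and 36 for calcium progression. All progression times exceed 30, so the imputed date cannot reach the first response. Off schedule it can: Appendix 11 sets no minimum interval for confirmation, and a response on 3 May, confirmed on 10 May, with progression on 31 May gives −2 days instead of 28. A confirmed RECIST response needs off-schedule progression exactly 29 days after first response, on a 31st, and then gives −1 day.

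**7. With a lower bound.** Using the later of the 1st and the day after the last progression-free assessment, 0 of 365 dates fall on or before that assessment at any gap tested from 1 to 70 days.

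**The case against.** The strongest reply is that the rule will almost never matter. RECIST progression takes the date of a scan, and myeloma progression rests largely on dated laboratory tests or imaging, so a missing day should be unusual. Section 8 opens permissively: "The following conventions may be used for imputing partial dates for analyses requiring dates". Best overall response and duration of response are by-subject listings (Protocol Section 10.3.1, SAP Section 7.5). The visit-level tumor evaluations and the M-protein and immunofixation results are listed too, so an impossible order would be visible.

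Most of this stands, and it sets the low priority. It does not remove the defect. The progression item itself says its conventions will be used, and a contradiction visible in a listing still has no stated resolution.

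A reader might also infer more than the documents support:

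- **That scheduled testing can give a negative duration.** It cannot, as step 6 shows; an off-schedule assessment is required.
- **That responses are deleted in C2.** The window closing at progression is written for RECIST only. For myeloma, loss of a response is an inference about how confirmation would be programmed.
- **That one lost responder in a cohort of 6 costs 1/6, or 17 points, of response rate.** The SAP defines a response rate, but Section 7.5 specifies listings and tabulates no rate.
- **That 8.0% is the share with progression before response.** It includes same-day ties and, in a scheduled C2 sequence, describes confirmation and progression, not first response and progression.

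**Conclusion.** The concern holds in a limited form. The check on an imputed progression date is on the wrong side, and the SAP's own death-date rule shows the missing bound. Imputed progression can precede a confirmatory or progression-free assessment in C2 on the planned tests, and in solid tumors only with a confirmatory scan at about 4 weeks or an off-schedule scan.

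The percentages are conditional on the day being missing and assume progression dates spread evenly over the calendar. The documents give no rate of missing days; that it is low is an assumption. The result is an understated duration or an apparently unconfirmed RECIST response in an occasional listing row. No primary endpoint or planned test is affected. This is a minor correction, worth making because it removes a decision that would otherwise be taken with the data in view.

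**What to change.** Replace the missing-day rule for on-study progression in SAP Section 8 with:

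> If only the day is missing, the progression date is the later of the 1st of the reported month and the day after the last evaluable assessment without progression that precedes the reported progression, not later than the end of the reported month; if the death date is complete, the earlier of that date and the death date is used.

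The restriction to preceding assessments is needed because Protocol Section 7.4.4 allows combination treatment beyond progression in solid tumors, and Section 9.1.1.1 requires scans to continue during it. Without the restriction, a later scan without progression could push the imputed date past the true one. Since the day is unknown, visit order should identify which assessments precede. The end-of-month limit keeps the date within the month recorded.

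The cost is one SAP sentence and a small change to the derivation program. Complete dates are unaffected.

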9 CONTENT OF REPORTS

The complete list of analyses contributing to the clinical study report is given in the Data Presentation Plan.

10 DOCUMENT HISTORY

Table 10-1: Document History

Version Number		Description
1.0		Initial version
2.0		The SAP was updated to align IO core SAP Ver 1.0.
3.0		Remove efficacy list only for MM cohort

[REDACTED]

[REDACTED]

[REDACTED]
